9.3.1. Special Considerations for Dosing, Including Inability to Take Medication Orally

It is imperative that study subjects take study drug as scheduled without missing doses. Under certain circumstances, when a subject cannot take or absorb BCX9930 (including acute illness with vomiting, dysphagia due to symptomatic hemolysis, and unplanned circumstances requiring hospitalization), there are provisions that can be taken.

For acute vomiting, treatment of nausea and/or vomiting with an oral, orally dissolving, or rectal suppository anti-emetic 30 minutes to an hour (as a suggestion) before attempting to swallow the BCX9930 tablets could be attempted. If a subject vomits after receiving a dose of BCX9930, the subject may be redosed (ie, take two new tablets) if the intact tablets or pieces of the tablets are seen in the vomitus (vomit contents).

Please refer also to the IMP manual for specific instructions.

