7.3. Treatment Dosing

The protocol-specified dose prior to this amendment was 500 mg BCX9930 BID. Under this amendment, subjects will take 400 mg BCX9930 BID orally .

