9.3. Treatment Compliance

For subjects who have had a dose interruption since the previous BCX9930 study, the first dose on Day 1 will be given in the clinic. All other doses and all doses for subjects continuing from the prior study without interruption, will be taken at home during the dosing period following the instructions provided by the study site staff. BCX9930 may be taken with or without food.

Where possible, the BCX9930 doses should be taken at the same times each day as close as possible to 12 hours apart (eg. 8:00 AM and 8:00 PM). Consideration should be given to strategies that will help reinforce these behaviors, such as asking subjects to voluntarily set up reminder alarms on their mobile phones or at their homes to remind them to take their doses, at least until they become adjusted to their new treatment regimen. Investigators should remind participants who regularly miss doses of BCX9930 about the importance of treatment compliance.

In-Clinic Dosing:

Investigational product administered in the clinic will be given directly by the investigator, or qualified staff member, under medical supervision to confirm compliance. The date and time of the administered dose in the clinic will be recorded in the subject's source documents and eCRF.

At-Home Dosing:

Subjects will be provided instructions for taking daily doses of investigational product at home, including frequency and time of administration. Subjects will be instructed to maintain approximately the same dosing interval between study drug doses each day.

Missed Doses:

Ideally, BCX9930 doses should be taken 12 hours apart at the same times each day without missing doses. If a subject does not take a BCX9930 dose at the scheduled time, the missed dose can be taken up to 6 hours after the scheduled dose time. If more than 6 hours has passed, the missed dose should not be taken. Regardless of whether the missed dose was made up, dosing should resume with the next dose taken at the scheduled time. For example, a subject who normally takes the BCX9930 doses at 8:00 AM/PM each day can take a missed morning dose as late as 2:00 PM with the evening dose administered on schedule at 8:00 PM. A missed evening dose can be taken as late as 2:00 AM the next day, with the next dose taken on schedule at 8:00 AM.

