10. STUDY DRUG MATERIALS AND MANAGEMENT

10.1. Study Drug

BCX9930 is a small molecule inhibitor of Factor D. The IMP will be supplied by BioCryst as 100, 200, and/or 250 mg tablets to allow for dose adjustments if needed for the safety management of the subject.

The active ingredient for this study is BCX9930, supplied by BioCryst. BCX9930 is a white or off-white powder.

The IMP will be administered by the oral route.

Additional details for the chemical and physical characteristics of BCX9930 may be found in the IB and IMP Manual.

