10.5. Administration

Subjects will take BCX9930 orally, either with or without food. Subjects will be treated for up to 144 weeks. Subjects should be encouraged to maintain an every-12-hour regimen and reminded of the importance of adherence to the dose schedule.

Subjects will take 400 mg BCX9930 BID. Throughout treatment with BCX9930, subjects should maintain adequate hydration to prevent the formation of highly concentrated urine.

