10.5.1. Treatment Interruption and Dose Reduction

Treatment interruption or dose reduction as a result of investigator management of AEs potentially related to study drug is permissible with appropriate monitoring for potential hemolysis as described in Section 13.9.5.4. Dose reduction should be done in consultation with the sponsor medical monitor (or designee). Any treatment interruption or dose reduction will be recorded in the eCRF and source documents, including the reason for the interruption or reduction. Resumption of study drug administration is also permissible upon resolution of the event, as assessed by the investigator, with a plan for monitoring of the subject for recurrence of the AE, as appropriate. See Section 10.5.2 for potential dose tapering options.

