13.9.5.3. Renal Events: Monitoring, Evaluation, and Discontinuation Criteria

There are multiple potential reasons that sCr can increase in those with PNH, including hemolysis. For subjects who have a confirmed treatment-emergent increase in sCr, evaluations to investigate potential etiology should be chosen considering baseline renal function, history of

prior renal events including those due to PNH, other comorbidities, concomitant medications, and other relevant factors. In addition:

- For all subjects, ensure adequate hydration, stop or substitute potentially nephrotoxic medications, and evaluate for tuberculosis if sterile pyuria is present if potential exposure
- For treatment-emergent increases in sCr > ULN confirmed by repeat testing, notify sponsor medical monitor
- A renal ultrasound with doppler should be considered to exclude renal vein thrombosis or other incidental causes
- Subject data may be reviewed by the NRMWG for additional recommendations, including dose reduction, interruption of dosing, and permanent discontinuation
- If a biopsy is performed, a redacted copy of the biopsy report and available images (whole slide images of light microscopy or electron microscopy specimens, immunofluorescence, immunohistochemistry, etc.) should be made available

Table 6 provides additional guidance based on sCr levels.

Table 6: Actions Based on Serum Creatinine Levels

sCr > ULN but $\leq 1.5 \times$ ULN	
 • Assessment frequency based on the magnitude of the sCr rise until sCr \leq ULN (ie, every 2 to 4 weeks). • Consider evaluation by nephrologist
sCr > $1.5 \times$ ULN but < $3 \times$ ULN	
 • Assessment frequency weekly until sCr \leq ULN • Evaluation by nephrologist
sCr $\geq 3 \times$ ULN	
 • BCX9930 should be discontinued, with taper (see Section 10.5.2), after confirmation • If hemolysis or any other potentially reversible cause is suspected, contact sponsor medical monitor

Abbreviations: sCr = serum creatinine; ULN = upper limit of normal.

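### The redose after vomiting is fixed at two tablets, which equals the assigned dose only when that dose is taken as two tablets

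*Protocol*

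**What the plan says.** Section 9.3.1 of the protocol covers subjects who vomit after a dose. If whole tablets or fragments are visible in what was vomited, "the subject may be redosed (ie, take two new tablets". No strength or milligram amount is attached. The section ends: "Please refer also to the IMP manual for specific instructions".

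The dosing sections around it are more flexible:

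- Section 10.5 gives the current dose: "Subjects will take 400 mg BCX9930 BID".
- Section 7.3 gives the previous one: "The protocol-specified dose prior to this amendment was 500 mg BCX9930 BID".
- Section 10.1 supplies the drug as "100, 200, and/or 250 mg tablets to allow for dose adjustments if needed for the safety management of the subject".
- Section 10.5.1 says that "dose reduction as a result of investigator management of AEs potentially related to study drug is permissible".
- Section 13.9.5.3 lets the nephrology working group make "additional recommendations, including dose reduction, interruption of dosing, and permanent discontinuation".

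The missed-dose rule in Section 9.3 has no tablet count. It says "the missed dose can be taken up to 6 hours after the scheduled dose time", which works for any regimen.

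**The concern.** The parenthesis in Section 9.3.1 opens with *ie*, so it defines a redose and does not merely give an example. A count of tablets fixes the amount of drug only if every subject takes two tablets per dose, and no visible text says so. Three strengths are permitted, and dose reduction is a foreseen event, with time to dose reduction a planned Kaplan-Meier summary (Protocol 14.3.5, SAP 9.1).

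Followed literally, the rule could go wrong in two directions. A subject reduced to a single tablet for safety could take twice the assigned amount as the replacement. A subject taking 400 mg as three or four tablets could replace only part of a lost dose, although Section 9.3.1 stresses not missing doses and Section 5.6.5 warns of hemolysis when treatment is interrupted. Most doses are taken at home (Section 9.3), and Section 9.3.1 does not ask the subject to contact the site before redosing.

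**Working it through.** **Inputs.** Redose: two tablets (9.3.1). Strengths: 100, 200 and 250 mg (10.1). Current dose: 400 mg (10.5). Previous dose: 500 mg (7.3). Reduced dose levels: none visible, so every dose below 400 mg here is an assumption.

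**Formula.** Redose share = (mg in two tablets of the kind the subject takes) / (mg assigned). Mixed-strength two-tablet doses are assumed to be replaced by the same two tablets.

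**The plan's own count.** Two tablets reproduce the standard dose when taken as 2 x 200 mg: (200 + 200)/400 = 100%. They also reproduce the earlier dose as 2 x 250 mg: (250 + 250)/500 = 100%.

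**All ways to make 400 mg.** A 250 mg tablet cannot be part of a 400 mg dose, because the remaining 400 − 250 = 150 mg cannot be made from these strengths. That leaves three combinations.

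| 400 mg taken as | Tablets | Two-tablet redose | Share |
|---|---|---|---|
| 2 x 200 | 2 | 400 mg | 400/400 = 100% |
| 200 + 2 x 100 | 3 | 200 or 300 mg, depending on which two | 200/400 = 50% or 300/400 = 75% |
| 4 x 100 | 4 | 200 mg | 200/400 = 50% |

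One of the three matches.

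**Assumed reduced doses (all combinations below 400 mg).**

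| Dose taken as | Assigned | Two-tablet redose | Share |
|---|---|---|---|
| 1 x 100 | 100 mg | 200 mg | 200% |
| 1 x 200 | 200 mg | 400 mg | 200% |
| 1 x 250 | 250 mg | 500 mg | 200% |
| 2 x 100 | 200 mg | 200 mg | 100% |
| 200 + 100 | 300 mg | 300 mg | 100% |
| 250 + 100 | 350 mg | 350 mg | 100% |
| 3 x 100 | 300 mg | 200 mg | 67% |

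Every two-tablet regimen matches, every single-tablet regimen is doubled, and every regimen of three or more tablets is under-replaced. These are replacement amounts, not absorbed exposure.

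**Link to the analysis.** The only connection is compliance, which SAP 7.6 computes from tablets dispensed minus tablets returned. Any redose adds tablets to that numerator, however the redose is defined, so the wording at issue does not change a planned analysis in any material way.

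**The case against.** The strongest reply is that no mismatching regimen is documented. SAP 3.6 moves subjects on lower or higher doses to 400 mg BID, a 200 mg tablet is available, and the range of strengths is described as being for adjustment, not as alternative ways to build the standard dose. Two tablets may therefore be right for nearly everyone. Section 9.3.1 also sends sites to the IMP manual, which may give dose-specific instructions. The taper text in Section 10.5.2 and much of the dose rationale in Section 5.5.2 are blacked out, so dose levels may be stated there.

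The harm also looks limited. Redosing is optional, and dose reductions are made in consultation with the sponsor medical monitor. Doubling a single tablet gives at most 500 mg, the earlier protocol dose, although anything already absorbed would add to it. A full repeat could also overshoot in a subject who had absorbed part of the dose.

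Most of this stands as a limit on the size and likelihood of the problem. It does not make the count correct for regimens that the protocol permits. The IMP manual is cited as a further source, so it supplements the stated count without replacing it; a dose-specific manual would conflict with the protocol for those regimens. The overshoot argument applies equally to the present rule in the 2 x 200 mg case, where two tablets are already a full repeat.

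**Conclusion.** The point holds as a conditional one. The two-tablet definition equals the assigned dose only for two-tablet regimens. Elsewhere the replacement would be 50% to 75% of a 400 mg dose taken as three or four tablets, 67% of an assumed 3 x 100 mg dose, and 200% of an assumed single-tablet dose.

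This rests on the listed strengths being dispensed in those combinations, which the protocol permits but the documents do not show, and on the rule being followed literally. Whether the IMP manual already resolves it cannot be checked here. The practical effect is small: one optional dose at a time, with unknown absorption. A doubled 1 x 200 mg dose is only the standard 400 mg. The doubled 1 x 250 mg case would return the subject to the 500 mg that the amendment reduced. The change is worth considering as a low-priority correction to an operative dosing instruction.

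**What to change.** In Section 9.3.1, replace the parenthesis with *(ie, repeat the full currently assigned dose)*, and confirm that the IMP manual says the same. This leaves the 2 x 200 mg case unchanged, is right for every permitted regimen, and brings the rule into line with the missed-dose wording in Section 9.3.

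The cost is one phrase and one check of the manual. Because Section 17.1 requires amendments to be agreed and formally documented, the sensible course is to include it in the next amendment.

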9.4. Randomization and Blinding

This is an open-label, non-randomized study. All subjects enrolled in the study will receive BCX9930 orally for up to 144 weeks, until drug is available by another mechanism (eg, expanded or market access) or until the Sponsor discontinues development of the product for PNH, whichever comes first.

9.5. Vaccination Requirements, and Vaccinations during Study, and Prophylactic Antibiotic Coverage

Unless local guidelines are more stringent, the Advisory Committee on Immunization Practices (ACIP) recommendations for meningococcal vaccination and ACIP guidance for altered immunocompetence (including complement inhibition therapy) should be followed ([Mbaeyi 2020](#), [Kroger, Bahta, et al. 2021](#)). For vaccines against serogroups A, C, W, and Y, a booster vaccine should be given every 5 years while on complement inhibitor therapy; the available vaccines are interchangeable. For vaccines against serogroup B, a booster vaccine should be given 1 year after the series completion and every 2 to 3 years thereafter; the available vaccines are not interchangeable ([Mbaeyi 2020](#)).

Investigators will review each subject's vaccination status at periodic intervals to ensure that any needed booster vaccinations are administered at the optimal timing during the study. Please contact the sponsor medical monitor or designee for any questions.

If a live vaccine needs to be given during the study, please contact the sponsor medical monitor or designee.

Local treatment guidelines should be followed for prophylactic antibiotic therapy for patients with PNH at the discretion of the investigator for those receiving treatment with complement inhibition.

10. STUDY DRUG MATERIALS AND MANAGEMENT

10.1. Study Drug

BCX9930 is a small molecule inhibitor of Factor D. The IMP will be supplied by BioCryst as 100, 200, and/or 250 mg tablets to allow for dose adjustments if needed for the safety management of the subject.

The active ingredient for this study is BCX9930, supplied by BioCryst. BCX9930 is a white or off-white powder.

The IMP will be administered by the oral route.

Additional details for the chemical and physical characteristics of BCX9930 may be found in the IB and IMP Manual.

10.2. Study Drug Packaging and Labeling

The study drug will be packaged in the appropriate size bottle. Each bottle will be labeled with the information required per local law and may include: Sponsor name, study protocol number, description of the contents, a statement regarding the investigational (clinical trial) use of the study drug and expiry date.

10.3. Study Drug Storage

Study drug will be stored between 15°C and 25°C (room temperature).

10.4. Study Drug Preparation

No study drug preparation is required. Tablets will be taken from the provided bottles.

10.5. Administration

Subjects will take BCX9930 orally, either with or without food. Subjects will be treated for up to 144 weeks. Subjects should be encouraged to maintain an every-12-hour regimen and reminded of the importance of adherence to the dose schedule.

Subjects will take 400 mg BCX9930 BID. Throughout treatment with BCX9930, subjects should maintain adequate hydration to prevent the formation of highly concentrated urine.

10.5.1. Treatment Interruption and Dose Reduction

Treatment interruption or dose reduction as a result of investigator management of AEs potentially related to study drug is permissible with appropriate monitoring for potential hemolysis as described in Section 13.9.5.4. Dose reduction should be done in consultation with the sponsor medical monitor (or designee). Any treatment interruption or dose reduction will be recorded in the eCRF and source documents, including the reason for the interruption or reduction. Resumption of study drug administration is also permissible upon resolution of the event, as assessed by the investigator, with a plan for monitoring of the subject for recurrence of the AE, as appropriate. See Section 10.5.2 for potential dose tapering options.

10.5.2. Dose Tapering

In the event of permanent discontinuation of BCX9930, [REDACTED]
[REDACTED]
[REDACTED]
[REDACTED]
[REDACTED]
[REDACTED]
[REDACTED]
[REDACTED]
[REDACTED]
[REDACTED]

The decision to taper the dose and duration of any taper will be based on the investigator’s medical judgement, taking into account the reason for discontinuation of the drug, the severity of

any reported signs or symptoms, and/or any reported worsening of signs or symptoms. The tapering schedule should be discussed with the sponsor medical monitor (or designee), ideally prior to implementation, and adjusted, as appropriate, for the individual subject.

10.6. Study Drug Accountability

The Investigator must maintain accurate records on a drug accountability form of the disposition of all study drugs received from the Sponsor, directly administered to the subject (including date and time) or dispensed to the subject. At the end of the study, information describing study drug supplies (eg, lot numbers) and disposition of supplies must be provided, signed by the Investigator or designee, and collected by the study monitor.

10.7. Study Drug Handling and Disposal

All medication not administered and used packaging materials will be returned to the Sponsor or destroyed on site as instructed by the Sponsor following IMP accountability by the study monitor, abiding by appropriate Standard Operating Procedure at the participating institution.

11. STUDY CONDUCT

11.1. Overview

This is an open-label, non-randomized study to evaluate the long-term safety and effectiveness of daily oral BCX9930.

Subjects will be eligible to receive study drug (BCX9930) for up to 144 weeks, until drug is available by another mechanism (eg, expanded or market access) or until the Sponsor discontinues development of the product for PNH (See Section 7.4), whichever comes first. Study drug will be discontinued for subjects who are deriving no clinical benefit, are intolerant of study drug, or experience an unacceptable drug-related TEAE as defined in more detail in Section 7.4. The Study will be discontinued if ongoing regulatory or Institutional Review Board/Ethics Committee (IRB/EC) approval is withdrawn, or in the event that technical or logistical factors prevent the ongoing conduct of the study. Subjects who discontinue study drug will have a minimum of 3 days hemolysis testing and then return to the clinic for an end-of-study visit 3 weeks after the last dose of study drug.

11.2. Schedule of Assessments

The schedule of assessments for this study is presented in [Table 4](#) and procedures are described below. Where possible, it is preferred that procedures are performed in the following sequence during each clinic visit:

1. Questionnaires
2. 12-lead ECG
3. Blood pressure (BP), temperature, and pulse rate
4. Blood sampling; the preferred order for blood sampling is:

- a. Hematology
- b. Coagulation
- c. Clinical chemistry and other laboratory assessments
- d. PK blood sample

Table 4: Study Design and Schedule of Assessments

Assessment	Screening Period ^a	Baseline Visit ^b	Treatment Period (Visit Schedule)		Unscheduled Visit Following BTH (within 48 hrs or next working day)	Discontinuation of Study Drug	End of Study Assessment
	Screening Visit (Up to Day -28)	(Day 1)	Week 4 and Every 4 wks up to Wk 96 ^c (± 3 days)	Week 96 and Every 8 wks Until Wk 144 ^d (± 6 days)		Hemolysis Monitoring for at least 3 Consecutive Days ^e	3 Weeks (± 3 Days) After Last Dose of Study Drug
Informed consent ^f	X	X					
Inclusion-exclusion criteria	X	X					
Medical and medication history ^g	X	X					
Weight/height/BMI ^h	X	X	X	X			X
Physical examination ⁱ	X	X	X	X	X	X	X
ECG ^j	X	X	X	X			X
Pregnancy test (women) ^k	X	X	X	X			X
FSH test (women) ^l	X	X					
Vital signs	X	X	X	X	X	X	X
Clinical chemistry ^m /hematology/coagulation/urinalysis with microscopy ⁿ /iron, folate, vitamin B ₁₂ status labs ^o	X	X	X	X	X ^p	X ^p	X
Urine for biomarkers ^q			X	X	X	X	X

Abbreviations: AE = adverse event; BID = twice daily; BTH = breakthrough hemolysis; BMI = body mass index; ECG = electrocardiogram; FSH = follicle-stimulating hormone; FACIT = Functional Assessment of Chronic Illness Therapy; IMP = investigational medicinal product; PD = pharmacodynamic; PK = pharmacokinetic; PNH = paroxysmal nocturnal hemoglobinuria; QLQ-AA/PNH = Quality of Life Questionnaire for Patients with Aplastic Anemia/PNH; RBC = red blood cell; TSQM = Treatment Satisfaction Questionnaire for Medication; WBC = white blood cell.

- ^a Screening visit is required for subjects who have interrupted study drug for > 30 days.
- ^b The baseline visit should be within 28 days of the screening visit. For subjects directly rolling over from another BCX9930 study without treatment interruption, the final on-treatment visit in the prior BCX9930 study will be considered the baseline visit for this study.
- ^c Visits should be every 4 weeks until a subject has completed a total of 96 weeks on treatment with BCX9930 (ie, weeks in this study plus weeks in the previous study).
- ^d Subjects will sCr elevations will be required to complete additional assessments to monitor for potential renal toxicity at the investigational site, at a remote laboratory more convenient for the subject, or via a home health service (where permitted and available) as indicated in Section 11.3.4.1 and Section 13.9.5.3.
- ^e Monitoring for the onset of hemolysis will be conducted after each subject stops BCX9930 treatment. Depending on the results, additional hemolysis testing may continue.
- ^f Informed consent will be signed at the screening visit for subjects requiring a screening visit and will be signed for all other subjects at the baseline visit or final on treatment visit in the prior study (which serves as the subject's baseline visit in this study).
- ^g Medical and medication history should include vaccination history status, assess risk of exposure, and arrange for any appropriate vaccinations to be administered based on local recommendations as well as individual subject considerations.
- ^h BMI calculation and height at screening; weight is to be recorded at each in-clinic visit.
- ⁱ Full physical examinations will be performed at screening and baseline; symptom-directed physical examinations will be performed at all post-baseline visits.
- ^j All ECGs during the study will be single assessments. ECGs will be conducted every 12 weeks up to Week 96 (ie, Weeks 12, 24, 36, 48, 60, 72, 84, and 96) and every 24 weeks thereafter (ie, Weeks 120 and 144) during the treatment period.
- ^k For women of childbearing potential, a serum pregnancy test will be administered at screening; urine pregnancy tests will be assessed at all subsequent visits. Starting at Week 100, women of childbearing potential will start performing urine pregnancy tests at home every 4 weeks (i.e., in between clinic visits). The results will be recorded by the site. If the urine pregnancy test is positive, the subject should contact the site immediately.
- ^l FSH will be measured at screening for any woman post-menopausal ≤ 2 years (this may be omitted if menopausal status was demonstrated with elevated FSH in the prior study). For women who do not undergo a screening visit, FSH may be assessed at baseline. In this case, the subject must have a negative urine pregnancy test at baseline prior to receiving study drug.
- ^m Cholesterol and triglycerides will be measured every 12 weeks up to Week 96 (ie, Weeks 36, 48, 60, 72, 84, and 96) and every 24 weeks thereafter (ie, Weeks 120 and 144).
- ⁿ Urine microscopy will be performed on urine collected at investigative site visits (and, where possible, at remote visits where the lab has appropriate on-site testing capability). Urine microscopy should be performed using the site's local laboratory (assuming appropriate on-site testing capability exists) in lieu of the central laboratory.
- ^o Weeks 48, 96, and 144 only.
- ^p Only limited hematology and clinical chemistry parameters measured as per Section 11.3.5 and Section 11.3.6.
- ^q Urine will be collected at investigative site visits (ie, excluding remote visits) and aliquots frozen for possible future analysis of urine biomarkers.
- ^r Completed at all treatment visits through Week 96 only.
- ^s Every 6 months through Week 96 only (ie, Weeks 24, 48, 72, and 96 only).

^t Though Week 96 only (ie, at Weeks 12, 24, 48, 72, and 96 only).

^u Single PK and PD sample collected 48 hours after treatment discontinuation.

^v Spot urine samples will be collected for analysis of the concentration of BCX9930 and metabolites at investigational site visits (ie, excluding remote visits).

^w The protocol-specified dosing regimen prior to this amendment was 500 mg BCX9930 BID. Under this amendment, subjects will take 400 mg BCX9930 BID. The IMP will be supplied by BioCryst as 100, 200, and/or 250 mg tablets to allow for dose adjustments if needed for the safety management of the subject.

^x BCX9930 dosing should continue following BTH.

